6.3.2 Treatment assignment, randomization

At the Baseline Visit, all eligible subjects will be randomized to one of the treatment arms via the Novartis Interactive Response Technology (NIRT). After confirming that the subject fulfills all the inclusion/exclusion criteria, the Investigator or delegate will contact the NIRT and randomize the subject. The NIRT will assign a randomization number to the subject and allocate the subject to a treatment arm. The treatment allocation will be confirmed in the NIRT and communicated to the Investigator or designee, who will dispense the medication accordingly.

The randomization numbers will be generated using the following procedure to ensure that treatment assignment is unbiased from subjects and Investigator staff. A subject randomization list will be produced by the NIRT provider using a validated system that automates the random assignment of subject numbers to randomization numbers. These randomization numbers are linked to the different treatment arms.

The randomization scheme for subjects will be reviewed and approved by a member of the Randomization Office.

6.4 Treatment blinding

Treatment will be open to subjects, Investigator staff, and the clinical trial team.

The assessment of all efficacy endpoints (primary and exploratory) will be performed by blinded independent clinicians, and pathologists/researchers.

6.5 Dose escalation and dose modification

Dose adjustments and/or interruptions are not permitted.

6.6 Additional treatment guidance

6.6.1 Treatment compliance

All doses of study treatment administered will be recorded on the appropriate Dosage Administration Record eCRF page. Subject compliance with study treatment should be assessed by qualified study site personnel at each study visit using the study kits and documentation regarding study treatment dispensation and administration.

Compliance will also be assessed continuously by Novartis study personnel during the conduct of the study using medication kits and the corresponding documentation. Study treatment doses and the corresponding dates of self-administration at home should be documented in a self-administration log. Subjects will be required to return the self-administration log as well as all dispensed study treatment at every visit for a compliance check.

The Investigator must promote compliance by instructing the subjects to take the study treatment exactly as prescribed and by stating that compliance is necessary for the subject's safety and the validity of the study. The subject must also be instructed to contact the Investigator if he/she is unable for any reason to take the study treatment as prescribed.

6.7 Preparation and dispensation

Each study site will be supplied with study drug in packaging as described under investigational and control drugs section.

6.7.1 Handling of study treatment and additional treatment

6.7.1.1 Handling of study treatment

Study treatment must be received by a designated person at the study site, handled and stored safely and properly and kept in a secured location to which only the Investigator and designated site personnel have access. Upon receipt, all study treatment must be stored according to the instructions specified on the labels. Clinical supplies are to be dispensed only in accordance with the protocol. Technical complaints are to be reported to the respective Novartis Country Organization Quality Assurance.

[figure not shown]
Medication labels will be in the local language and comply with the legal requirements of each country. They will include storage conditions for the study treatment but no information about the subject except for the medication number.

The Investigator must maintain an accurate record of the shipment and dispensing of study treatment in a drug accountability log. Monitoring of drug accountability will be performed by monitors during site visits or remotely and at the completion of the study. Subjects will be asked to return all unused study treatment and packaging at the end of the study or at the time of discontinuation of study treatment.

At the conclusion of the study, and as appropriate during the course of the study, the Investigator will return all unused study treatment, packaging, drug labels, and a copy of the completed drug accountability log to the Novartis monitor or to the Novartis address provided in the Investigator folder at each site.

6.7.2 Instruction for prescribing and taking study treatment

Study treatments will be administered subcutaneously throughout the study (Table 6-3). The first dose will be administered under supervision at the study site. Self-administration at home will be allowed from the second dose or when the subject, after being instructed and trained, is qualified to self-inject at the discretion of the Investigator.

Study treatments must be injected in never-lesional areas of the skin to one of the following body regions: front of thighs, or lower abdomen (but not the area 2 centimeters around the navel). Investigator/qualified site staff can also inject in the outer upper arms. Study treatment should not be injected into areas where the skin is tender, bruised, red, scaly or hard, and areas with scars or stretch marks should be avoided. As far as possible, the injection site should be changed from administration to administration throughout the study.

Detailed instructions on the self-administration of the study treatment will be described in the instructions for use and provided to each subject.

Subjects will be asked to return all used and unused medication and packaging at each scheduled study visit.

Secukinumab 300 mg s.c.

Secukinumab will be administered at Baseline, Weeks 1, 2, 3, 4 and then every 4 weeks until Week 12 inclusive. After Week 4 (the last weekly administration of secukinumab), the subjects will be contacted by the Investigator or staff and be reminded to start the self-administration every 4 weeks instead of every week until Week 12.

Guselkumab 100 mg s.c.

Guselkumab will be administered subcutaneously at Baseline, Weeks 4, and 12.

Table 6-3 Study treatment administration schedule

Treatment	Baseline	Week 1	Week 2	Week 3	Week 4	Week 8	Week 12
Secukinumab	X	X	X	X	X	X	X
Guselkumab	X				X		X

7 Informed consent procedures

Eligible subjects may only be included in the study after providing (witnessed, where required by law or regulation), Institutional Review Board/Independent Ethics Committee (IRB/IEC)-approved informed consent.

If applicable, in cases where the subject's representative gives consent (if allowed according to local requirements), the subjects must be informed about the study to the extent possible given their understanding. If the subjects are capable of doing so, they must indicate agreement by personally signing and dating the written informed consent document.

Informed consent must be obtained before conducting any study-specific procedures (e.g., all of the procedures described in the protocol). The process of obtaining informed consent must be documented in the subject source documents.

Novartis will provide to Investigators in a separate document a proposed informed consent form that complies with the ICH Good Clinical Practice (GCP) guidelines and regulatory requirements and is considered appropriate for this study. Any changes to the proposed consent form suggested by the Investigator must be agreed by Novartis before submission to the IRB/IEC.

Information about common side effects already known about the investigational drug can be found in the Investigator's Brochure (IB). This information will be included in the subject informed consent and should be discussed with the subject during the study as needed. Any new information regarding the safety profile of the investigational drug that is identified between IB updates will be communicated as appropriate, for example, via an Investigator notification or an aggregate safety finding. New information might require an update to the informed consent and then must be discussed with the subject.

Women of childbearing potential must be informed that taking the study treatment may involve unknown risks to the fetus if pregnancy were to occur during the study and agree that in order to participate in the study they must adhere to the contraception requirements.

Male subjects must be informed that if a female partner becomes pregnant while he is enrolled in the study, contact with the female partner will be attempted to request her consent to collect pregnancy outcome information.

[REDACTED]

[REDACTED]

A copy of the approved version of all consent forms must be provided to Novartis after IRB/IEC approval.

8 Visit schedule and assessments

Assessment schedule ([Table 8-1](#)) lists all of the assessments when they are performed. All data obtained from these assessments must be supported in the subject's source documentation.

Subjects should be seen for all visits/assessments as outlined in the assessment schedule or as close to the designated day/time as possible. Missed or rescheduled visits should not lead to automatic discontinuation. Subjects who prematurely discontinue the study for any reason should be scheduled for a visit as soon as possible, at which time all of the assessments listed for the final visit will be performed. At this final visit, all dispensed investigational product should be reconciled, and the AEs and concomitant medications recorded on the eCRF.

[REDACTED]

Table 8-1 Assessment schedule

Visit name	Screening	Baseline	End of study	Unscheduled
Visit number	1	2	3	-
Week	-4 to -1	-	16	-
Day	-28 to -1	1	112	-
Informed consent	X			
Inclusion/exclusion criteria	X	X		
Pregnancy test ²	X	X		
Randomization via NIRT		X		
Physical examination	X	X	X	X
Smoking history	X			
Medical history	X			
Relevant family history	X			
Demography	X			
Psoriasis medical and treatment history	X			
QFT	X			
Skin type	X			
Body temperature (°C)	X	X		
Height (cm)	X			
Weight (Kg)	X	X	X	
Vital signs	X	X	X	
Electrocardiogram	X			
Laboratory assessments	X		X	
Adverse events ³	X	X	X	X
Drug administration record		X	X	X
Concomitant medications	X	X	X	X
TCS of target plaque	X	X	X	X
Skin biopsies ██████████ ⁶		X	X	
Information on study completion			X	

Baseline Visit (Visit 2) should be conducted within 28 days of the Screening Visit (Visit 1).

Unscheduled visits can be decided by the Investigators according to their own clinical judgment and practice.

End-of-study assessments (Visit 3) should be conducted only on subjects who complete 4 to 16 weeks of treatment. There will be a \pm 2-day window for Visit 3 (Week 16)

- [REDACTED]
- 2) Performed on serum for women of childbearing potential
 - 3) SAEs collected up to 30 days after the last administration of study treatment

[REDACTED]

6) At Baseline, two 6-mm punch biopsies will be taken, one from the identified active plaque (TCS \geq 6) and one from never-lesional skin. At the End-of-study Visit, one biopsy will be taken from the same area of the plaque sampled at Baseline. Biopsies should be sampled from the trunk whenever possible to avoid scars in exposed areas of the body

8.1 Screening

Subject's eligibility for the study will be assessed at the Screening Visit (Day -28 to Day -1 before Baseline) and at the Baseline Visit (see [Table 8-1](#)).

Subjects who fail screening for any reason may be rescreened. There will be no restriction on the number of times a potential subject may be rescreened or on how much time must pass from the date of screen failure and the date of rescreening. Subjects who are rescreened must sign a new informed consent form and be issued a new subject number before any study-related assessment is performed or any data for the Screening Visit are collected for the subject under the new subject number.

The Investigator or qualified site staff will record all rescreenings on the Rescreening eCRF page and any applicable screening numbers the subject was issued prior to the current screening number. The date of the new informed consent signature must be entered on the Informed Consent eCRF page to correspond with the new screening subject number.

The Withdrawal of Consent eCRF page must be completed if consent was withdrawn during the Screening Visit before the subject was randomized.

8.1.1 Information to be collected on screening failures

Subjects who sign an informed consent form and subsequently are found to be ineligible prior to randomization will be considered screen failures. The reason for screen failure should be recorded on the appropriate eCRF page. The demographic information, informed consent, and inclusion/exclusion pages must also be completed for screen failures. No other data will be entered into the clinical database for screen failures, unless the subject experienced an SAE during the Screening Visit (see [Section 10.1.3](#) for reporting details). If the subject fails to be randomized, the NIRT must be notified within 2 days.

Subjects who are randomized and fail to start treatment, e.g., randomized in error, will be considered early terminators. The reason for early termination should be recorded on the appropriate eCRF page.

[REDACTED]

8.2 Subject demographics/other baseline characteristics

Subject demographics and baseline characteristics will be collected at the Screening Visit. Data to be collected on all subjects include: date of birth, age, sex, race, ethnicity, height, weight, and skin type (see [Section 16.2.1](#)).

8.2.1 Smoking history

The current and/or previous use of tobacco products will be recorded, as well as the estimated number of pack-years based on the approximate consumption per year. Non-smokers will be advised to not start smoking during the study.

8.2.2 Relevant medical history/current medical conditions

Relevant medical history and current medical conditions, not including psoriasis or psoriatic arthritis, prior to signing of the informed consent will be recorded in the Medical History eCRF page. Whenever possible, diagnoses and not symptoms will be recorded.

Subjects with inflammatory bowel disease will be eligible for the study but should be closely followed when randomized to secukinumab.

Significant findings that are observed after the subject has signed the informed consent form and that meet the definition of an AE must be recorded in the Adverse Event eCRF page.

8.2.2.1 Psoriasis medical and treatment history

Disease history will be collected at the Screening Visit. The information to be collected and entered in the Psoriasis History eCRF page and Prior Psoriasis Therapies eCRF page will include the following:

1. Date of first diagnosis of plaque psoriasis
2. Previous treatments of psoriasis (including previous use of biologic therapies, as well as phototherapy and/or photo-chemotherapy) and the reason for discontinuation of each therapy
3. Presence of psoriatic arthritis or ankylosing spondylitis (including questions on signs and symptoms captured in the eCRF) and the date of the first diagnosis by a physician

[figure not shown]
8.2.3 Prior and concomitant medications

Concomitant medications and prior medications taken within the 6 months preceding study enrollment will be captured at the Screening Visit, and updated at the Baseline Visit or subsequent visits.

8.2.4 Determination of tuberculosis status

Determination of TB status will be required at the Screening Visit and should be performed as defined by local guidelines. Tuberculosis status must be determined by medical history, signs, symptoms, and TB testing (QFT).

Any significant findings will be recorded in the Tuberculosis Assessment eCRF page and the Medical History eCRF page, as necessary.

8.2.4.1 QuantiFERON TB-Gold In-Tube assay

This test will only be used to screen the subject population for latent TB infection (Doherty et al 2008) and determine subject's eligibility for the study.

This blood-based assay is specific for Mycobacterium tuberculosis and is not influenced by previous bacillus Calmette-Guerin vaccination or exposure to other Mycobacteria species. In contrast to the purified protein derivative skin test, it is also insensitive to a booster effect, since the subject is not exposed to the vaccine. The assay measures the production of interferon-gamma and presents it relative to negative and positive control samples (Manuel and Kumar 2008).

The QFT will be supplied by the central laboratory. Details on the collection, shipment of samples and reporting of results by the central laboratory will be provided to Investigators in the laboratory manual.

1. If the test result is negative, the subject may be randomized
2. If the test result is positive, the Investigator should perform workup as per local guidelines (if a TB workup was conducted prior to the screening of the subject, results of the workup can be used to assess eligibility if the workup was conducted within 12 weeks prior to Randomization)
 - a. subjects positive for active TB per workup are not eligible for the study
 - b. subjects diagnosed with latent TB per workup may be randomized to the study if sufficient treatment has been initiated according to local routine clinical practice or guidelines and will be maintained for the prescribed duration
3. If the test result is indeterminate, it is recommended to repeat the test once
 - a. if the second test is negative, the subject may be randomized
 - b. if the second test is positive or indeterminate, the investigator should perform workup as per local guidelines (if a TB workup was conducted prior to the screening of the subject, results of the workup can be used to assess eligibility if the workup was conducted within 12 weeks prior to Randomization)
 - o subjects positive for active TB per workup are not eligible for the study
 - o subjects diagnosed with latent TB per workup may be randomized to the study if sufficient treatment has been initiated according to local routine clinical practice or guidelines and will be maintained for the prescribed duration

8.3 Efficacy

8.3.1 Total clinical score

The TCS will be assessed at all study visits as indicated in Table 8-1. At Baseline, it should be performed before the first administration of study treatment.

The TCS for each plaque will be determined (ideally by the same evaluator) as the sum of 3 scores: erythema (0-3), scaling (0-3) and infiltration (0-3) rated according to their severity as shown in Table 8-2. The TCS can range from 0 (all signs absent) to 9 (all signs severe).

Table 8-2 Assessments of total clinical score

Score	Intensity	Erythema	Scaling	Infiltration
0	No evidence	Normal skin color	No scaling	No infiltration
0.5	Doubtful or very mild			
1.0	Mild	Pink/light red	Slight roughness, mainly fine scales	Slight definite infiltration
1.5	Mild to moderate			
2.0	Moderate	Red	Coarse scaling	Moderate infiltration
2.5	Moderate to severe			
3.0	Severe	Intense red	Coarse, thick scales	Very marked infiltration

8.3.3 Skin biopsies

At Baseline, two 6-mm punch biopsies will be taken, one from the identified active plaque (TCS \geq 6) and one from never-lesional skin. At the End-of-study Visit, one biopsy will be taken from the same area of the active plaque sampled at Baseline.

After collection, biopsies will be transported within 24 hours to the laboratory for further processing using a Novartis delegated service provider.

Laboratory manuals will be provided with detailed information on sample collection, handling, and shipment. The sample collection date and exact time must be entered on the Sample Collection eCRF page.

8.3.4 Microscopic morphology of the skin plaque

[figure not shown]
[figure not shown]
General histopathology of the skin will be assessed by hematoxylin and eosin staining and epidermal proliferation and differentiation by immunohistochemical (IHC) staining of Ki-67 and keratin-16 positive nuclei. The quantification of positive cells will be performed at X 200 magnification and calculated per mm of skin length.

[figure not shown]
[figure not shown]
8.3.5 Infiltrating immune cells in the skin plaque

[figure not shown]
[figure not shown]
The number of infiltrating cells expressing IL-17A and IL-23R will be assessed by single-staining IF using IHC and immunofluorescence (IF) if needed, and will be counted per mm of skin length.

[figure not shown]
8.3.6 Composition of the inflammatory infiltrate in the skin plaque

[figure not shown]
Single or double staining (IHC/IF) will be used to identify different cell types in the immune infiltrate according to the following markers: T-cells (CD3, CD8); neutrophils (elastase); mastocytes (tryptase); dendritic cells (CD11c); macrophages (CD163); NK cells (CD56); NKT cells (CD3, CD56); T-resident memory cells (CD49, CD103). The number of cells per cell type will be counted per mm of skin length.

8.4 Safety

Safety assessments are specified in [Table 8-5](#) and [Table 8-6](#). For details on AE collection and reporting, refer to the AE section.

Table 8-5 Physical assessments

Assessment	Specification
Physical examination	
A complete physical examination will include the inspection of general appearance, skin, neck (including thyroid), eyes, ears, nose, throat, lungs, heart, abdomen, back, lymph nodes, and extremities, and the vascular and neurological systems. If indicated based on medical history and/or symptoms, rectum, external genitalia, breast, and pelvic will be examined.
 
In particular, will include recognition of enthesitis, dactylitis, and the patterns of joint, or nail involvement.
 
Information for all physical examinations must be included in the source documentation at the study site. Significant findings that are present prior to signing the informed consent must be included in the Medical History eCRF page. Significant findings made after the first administration of investigational drug, which meet the definition of an AE must be recorded on the Adverse Event eCRF page.

Vital signs	
Vital signs include measurements of blood pressure and pulse. After the subject has been sitting for 5 minutes, with the back supported and both feet placed on the floor, systolic and diastolic blood pressures will be measured 3 times using an automated validated device, e.g., OMRON, with an appropriately sized cuff. The repeat-sitting measurements will be made at 1-2 minute intervals and the mean of the 3 measurements will be used. If the available cuff sizes are not large enough for the subject's arm circumference, a sphygmomanometer with an appropriately sized cuff may be used.
 
If possible, assessments should be performed by the same study site staff member throughout the study.

Assessment	Specification
	
Normal blood pressure will be defined as systolic pressure of 90 to < 120 mmHg, and diastolic blood pressure of 60 to < 80 mmHg under the measurement conditions outlined above. Notable blood pressure findings will be hypertension (systolic blood pressure of \geq 140 mmHg and/or diastolic blood pressure of \geq 90 mmHg) or hypotension (systolic blood pressure of < 90 mmHg and/or a diastolic blood pressure of < 60 mmHg). A blood pressure indicative of prehypertension (systolic blood pressure of 120 to < 140 mmHg and/or diastolic blood pressure of 80 to < 90 mmHg) will not be regarded as notable (Whelton et al 2017).
 
A normal pulse rate will be defined as a rate of 60 to 100 beats per minute (bpm) under the measurement conditions outlined above. Notable pulse rate will be a rate below 60 bpm (bradycardia) or above 100 bpm (tachycardia).
 
Whether action needs to be taken to address notable vital signs will be decided by the Investigator, taking into account the overall status of the subject. No specific action is foreseen as part of the study protocol.

Height and weight	Height in cm and body weight (to the nearest 0.1 Kg in indoor clothing, but without shoes) will be measured.

8.4.1 Laboratory evaluations

A central laboratory will be used for the analysis of all specimens collected. Details on the collection, shipment of samples and reporting of results by the central laboratory will be provided to Investigators in the laboratory manual.

Clinically notable laboratory findings are defined in [Appendix 1](#).

Table 8-6 Laboratory assessments

Test category	Test name
Hematology	Hemoglobin, hematocrit, red blood cell count, white blood cell count with differential, and platelet count will be quantified.
Chemistry	Blood urea, creatinine, total bilirubin, alkaline phosphatase, international normalized ratio, sodium, potassium, chloride, calcium, phosphorous, total protein, albumin, uric acid, and lipid panel will be quantified.
Urinalysis	
The central laboratory will provide dipsticks to the sites for local analysis of urine. Dipstick analysis will measure specific gravity, albumin, protein, glucose and blood. Microscopy and white blood cell count and red blood cell count sediments will be assessed in case of an abnormal dipstick test. Only samples with abnormal dipstick will be assessed by the central laboratory and the results provided in loaded data.
 
Study sites should record the results in the source documentation.

Additional tests	
Pregnancy test	
A serum β-hCG test will be performed to all pre-menopausal women as shown in Table 8-1.
 
Any woman with a confirmed positive pregnancy test (hCG > 5 mIU/mL) during Screening will not be eligible for randomization.
 
Women of childbearing potential should use an effective method of contraception while on treatment, or longer if required by locally-approved prescribing information (e.g., 20 weeks after the last dose in the EU and countries where applicable for secukinumab).

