5.2 Exclusion criteria

Subjects meeting any of the following criteria are not eligible for inclusion in this study.

1. Forms of psoriasis other than chronic plaque-type (e.g., pustular, erythrodermic, and guttate psoriasis) at Screening or Baseline
2. Drug-induced psoriasis (i.e., new onset or current exacerbation from beta-blockers, calcium channel inhibitors or lithium) at Screening or Baseline
3. Previous treatment with more than one TNF α inhibitor or with IL-17A (including secukinumab), IL-17R or IL-23 (including guselkumab) inhibitors

4. Use of other investigational drugs within 4 weeks before enrolment, or within a period of 5 half-lives of enrollment/initiation of the study treatment, whichever is longer
5. Ongoing use of prohibited treatments (see [Section 6.2.2](#))
6. Known immunosuppression (e.g., AIDS) at Screening or Baseline
7. History of an ongoing, chronic, or recurrent infectious disease, or evidence of tuberculosis (TB) infection as defined by a positive QuantiFERON TB-Gold test In-Tube assay (QFT) at Screening. Subjects with a positive or indeterminate QFT test may participate in the study if a full tuberculosis workup (according to local practice/guidelines) is completed within 12 weeks prior to randomization and conclusively establishes that the subject has no evidence of active tuberculosis. If presence of latent tuberculosis is established, then treatment must have been initiated and maintained according to local guidelines prior to randomization (see [Section 8.2.4](#))
8. History of hepatitis B, hepatitis C, or HIV infection
9. History of congestive heart failure (NYHA functional classification \geq III) at Screening or Baseline
10. Uncontrolled hypertension (systolic \geq 160 mmHg, diastolic \geq 95 mmHg)
11. History of hypersensitivity to any of the study treatments or its excipients or to any human or humanized biological agents (antibody or soluble receptor) at Screening including reactions to local anesthetics required to perform skin biopsy
12. History or evidence of ongoing alcohol or drug abuse, within the last 6 months before Baseline
13. Any live vaccines (including nasal-spray flu vaccine) starting from 6 weeks prior to initial treatment administration and during the study period
14. Pregnant or nursing (lactating) women, where pregnancy is defined as the state of a female after conception and until the termination of gestation, confirmed by a positive human chorionic gonadotropin (hCG) laboratory test (> 5 mIU/mL)

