15. History of lymphoproliferative disease or any known malignancy or history of malignancy of any organ system treated or untreated within the past 5 years, regardless of whether there is evidence of local recurrence or metastases (except for skin Bowen's disease, or basal cell carcinoma or actinic keratosis that have been treated with no evidence of recurrence in the past 12 weeks; carcinoma *in situ* of the cervix or non-invasive malignant colon polyps that have been removed)
16. Underlying conditions (including, but not limited to metabolic, hematologic, renal, hepatic, pulmonary, neurologic, endocrine, cardiac, infectious or gastrointestinal) which in the opinion of the Investigator significantly immunocompromise the subject and/or places the subject at unacceptable risk for receiving an immunomodulatory therapy. In addition, current severe progressive or uncontrolled diseases which render the subject unsuitable for the study or put the subject at increased risk, including any medical or psychiatric condition which, in the Investigator's opinion, would preclude the participant from adhering to the protocol or completing the study per protocol
17. Inability or unwillingness to undergo study procedures, including venipunctures and skin biopsy

No additional exclusions may be applied by the Investigator in order to ensure that the study population will be representative of all eligible subjects.

6 Treatment

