8.4.4 Appropriateness of safety measurements

The safety assessments selected are standard for this indication/subject population.

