16.1 Appendix 1: Clinically notable laboratory values and vital signs

The following criteria will be used to define expanded limits and notable abnormalities of key laboratory tests. Notable values for blood pressure and pulse are presented in [Table 8-5](#).

Liver function and related variables

Total bilirubin:	> 2 x upper limit of normal (ULN)
Alkaline phosphatase:	> 2.5 x ULN

Renal function and electrolyte variables

Creatinine (serum):	> 1.5 x ULN
Potassium:	> 6 mmol/L or < 3 mmol/L
Sodium:	> 160 mmol/L or < 115 mmol/L

Urinalysis variable

Protein urine dipstick:	2+ (100 mg/dL)
-------------------------	----------------

Hematology variables

Hemoglobin:	≥ 20 g/L decrease from Baseline
Platelet count:	< lower limit of normal (LLN)
White blood cell count:	< 0.8 x LLN
Neutrophils:	< 0.9 x LLN
Eosinophils:	> 1.1 x ULN
Lymphocytes:	> 1.1 x ULN

16.2 Appendix 2

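### The scheduled laboratory panel and the liver limits in Appendix 1 omit ALT and AST, so aminotransferase elevations are neither screened for nor systematically detected in either arm

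*Protocol*

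**What the plan says.** Section 8.4.1 sends specimens to a central laboratory, and Table 8-6 names the tests. The chemistry row reads "Blood urea, creatinine, total bilirubin, alkaline phosphatase, international normalized ratio, sodium, potassium, chloride, calcium, phosphorous, total protein, albumin, uric acid, and lipid panel". It is one complete sentence with no redaction mark inside it.

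Appendix 1 (Section 16.1) has a block headed "Liver function and related variables" with two rows: total bilirubin and alkaline phosphatase.

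In Table 8-1 the row "Laboratory assessments" is marked at Screening and at End of study, but not at Baseline or at unscheduled visits. A note to the table says that End-of-study assessments "should be conducted only on subjects who complete 4 to 16 weeks of treatment".

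Section 8.4.4 justifies the whole set in one line: "The safety assessments selected are standard for this indication/subject population".

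Four provisions bear on the liver at entry:
- Exclusion criterion 8 removes subjects with "History of hepatitis B, hepatitis C, or HIV infection".
- Exclusion criterion 16 begins "Underlying conditions (including, but not limited to metabolic, hematologic, renal, hepatic" and goes on to other organ systems. It leaves the judgement of risk to the investigator.
- Section 8.2.4.1 provides that "subjects diagnosed with latent TB per workup may be randomized to the study if sufficient treatment has been initiated" and will be maintained.
- Table 6-2 permits methotrexate and retinoids up to 4 weeks before Baseline.

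Section 12.7 plans CTCAE-graded shift tables, from baseline to the worst on-treatment value, for key hematology and biochemistry tests.

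**The concern.** The protocol sets out to look at the liver. It measures several liver-related analytes, defines notable liver values and asks for an opinion on hepatic conditions before randomization. It leaves out the two enzymes that directly mark hepatocellular damage, although serum is already taken for chemistry at both time points.

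Two things are at stake. At entry, the investigator applies criterion 16 without a study aminotransferase result, in a population that may include recent methotrexate or retinoid users and subjects on treatment for latent tuberculosis. At analysis, the safety tables can say nothing about ALT or AST in either arm. A statistical analysis plan cannot repair this later, because it cannot tabulate what was never measured.

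**Working it through.** No stated figure depends on this point, so there is nothing to reproduce. The check compares the places that could supply an aminotransferase value.

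1. **Panel.** Table 8-6 has 14 chemistry entries. Those that reflect the liver are total bilirubin, alkaline phosphatase, INR, and albumin with total protein. Aminotransferases: 0 of 14.

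2. **Limits.** The liver block of Appendix 1 has 2 rows. Aminotransferases: 0 of 2. Two separate lists agree, so this is not a line dropped from one table or lost in text extraction.

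3. **Rest of the protocol.** ALT, AST and their synonyms appear nowhere else in the visible text. Section 8.4.1 refers to a laboratory manual, but for collection, shipment and reporting of results, not for the test list.

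4. **Scheduled values.** With 40 subjects (Section 12.9.1) and 2 sampling visits, there are at most 40 × 2 = 80 chemistry samples. The number with a planned aminotransferase result is 0. The End-of-study count will be below 40 if any subject stops before Week 4.

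5. **Would the values be usable?** Section 12 takes as baseline the last assessment on or before the start of treatment, which for laboratory tests is the Screening sample. Section 12.7 counts data as on-treatment up to 30 days after the last administration. In a completer dosed on schedule, the last dose is at Week 12 in both arms and the final visit at Week 16: (16 − 12) × 7 = 28 days, and at most 28 + 2 = 30 days with the visit window. The sample falls inside the on-treatment period, so an ALT or AST shift table could be filled with no change to the schedule.

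6. **Other routes to detection.**
- Adverse events are sought by non-directive questioning (Section 10.1.1), and a subject without symptoms has nothing to report.
- A laboratory abnormality can become an adverse event under Section 10.1.1 only if someone measures it.
- Section 14 allows extra safety assessments case by case, which does not produce data that can be compared between arms.

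**The case against.** The case on the other side has weight, and part of it stands.

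**The liver is not unmonitored.** A reader might infer that hepatocellular injury can be neither screened for nor detected. The protocol does not support that. Bilirubin, INR, albumin and alkaline phosphatase are measured at both visits. The physical examination covers eyes and abdomen (Table 8-5). Criteria 8 and 16 screen by history and judgement, and adverse events and case-by-case tests remain. What goes systematically unseen is an isolated enzyme rise without symptoms. This stands and sets the limit of the point.

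**Absence of hepatitis serology is not established.** Table 8-1 has redacted footnotes, so the visible schedule may be incomplete. No conclusion is drawn about serology.

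**No false safety claim is planned.** A reader might infer that the trial would report an absence of liver findings. The protocol nowhere plans such a statement. With zero events among 20 subjects, the exact one-sided 95% upper bound on the event rate is 1 − 0.05^(1/20) = 13.9%, so the statement would be weak even with ALT and AST measured.

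**There is no documented hepatic risk and no internal contradiction.** Sections 4.5.1.1 and 4.5.1.2 list no liver effect for either drug, the two laboratory lists agree, and criterion 16 names no test. All true. It makes the point one of safety data capture, not of error in a calculation or a rule. It does not explain the omission, for which Section 8.4.4 gives no reason.

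**The remedy is partial.** The only scheduled on-treatment sample comes after the last dose, so in completers it could not inform dosing. An abnormal Screening value would act only through criterion 16, since Section 5.2 bars further investigator exclusions. Both are correct, but a baseline and a post-treatment value for each evaluable subject are still gained.

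**Conclusion.** The point holds in a limited form. Followed as written, the protocol yields no scheduled ALT or AST value in either arm (0 of at most 80 samples), so aminotransferase elevations are neither screened for nor systematically detected and Section 12.7 cannot show them. Total bilirubin, alkaline phosphatase, INR and albumin/total protein are the only scheduled laboratory tests that reflect the liver.

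This rests on two assumptions. One is that the unredacted chemistry list is complete and no document outside the protocol adds analytes. The other is general clinical knowledge, not a figure from the protocol: aminotransferases can be raised while the measured liver tests are normal. How many of the 40 subjects would have such a rise cannot be estimated from the document.

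The primary endpoint, sample size, power and type I error are not affected. The change is worth making because it closes a gap in safety data at almost no cost, not because a result of the trial depends on it.

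**What to change.** - Add ALT and AST to the chemistry row of Table 8-6, on the samples already drawn at Screening and End of study and in the same central laboratory.
- Include both in the CTCAE-graded shift tables of Section 12.7.
- List both in the liver block of Appendix 1, with notable limits set by the sponsor.
- If the omission was deliberate, give the reason in Section 8.4.4.

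No eligibility threshold or stopping rule is proposed. The cost is two routine analytes, a few lines of protocol text and possibly a few more screen failures under criterion 16. No visit, blood draw or other procedure is added.
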